APPENDIX D: During-travel Questionnaire

During Travel Questionnaire

PARTICIPANT UNIQUE ID: _____

GROUP ID: _____

	Day 1	Day 2	Day 3	Day 4	Day 5
Please write the calendar date that corresponds to each day of your trip. Day 1 is your first day of arrival in the country.					
Number of tablets taken in the morning (maximum 4)					
Number of tablets taken in the afternoon/evening (maximum 4)					
Symptoms in the prior 24 hours (check off all that apply)	... 				
Fever					
Nausea					
Vomiting					
Loose stools (less than three in a 24 hour period)					
Diarrhea (three or more loose stools in 24 hours)					
Bloody diarrhea					
Constipation					
Dark or black stool					
Dark or black tongue					
Abdominal pain					
Abdominal cramps					
Urgency to relieve oneself (in reference to stool)					
Bloating					
Flatulence/gas					
Congestion/runny nose					
Sore throat					
Cough					
Rash					
Headache					
Dizziness					
Ringing in your ears					
Muscle pain/soreness					
Joint pain/swelling/redness					

Drowsiness (severe)					
Confusion					
Depression					
Other (list/describe):					
Medical care
Did you seek medical care for one or more of these symptoms? (Yes/No/Don't Know)	Y N D	Y N D	Y N D	Y N D	Y N D
→ If yes, where? (check the corresponding box(es))
A doctor's office					
Urgent care clinic (outpatient)					
Emergency room					
Hospital outpatient clinic setting					
Hospital inpatient ward – hospitalized					
Other (specify)					
→ Was your diagnosis travelers' diarrhea? (Yes/No/Don't Know)	Y N D	Y N D	Y N D	Y N D	Y N D
Have you started any medications in the past 24 hours? (Yes/No/Don't Know)	Y N D	Y N D	Y N D	Y N D	Y N D
→ If yes, what medication(s)?					
→ Please circle those that were provided for you at your pre-travel consultation with the study clinic.
What city(ies) and country(ies) have you been in during the past 24 hours? Please write answers to all questions in the corresponding box.					
Have you eaten any of the following in the past 24 hours? (Yes/No/Don't Know)
→ Fermented or pickled foods (e.g., bean paste, fish kimchi, etc.)	Y N D	Y N D	Y N D	Y N D	Y N D
→ Yogurt	Y N D	Y N D	Y N D	Y N D	Y N D
Did you have any diarrhea between completing the pre-travel questionnaire and arriving in the country? (Yes/No/Don't Know)	Y N D
Comments:					

PARTICIPANT UNIQUE ID: _____

GROUP ID: _____

	Day 6	Day 7	Day 8	Day 9	Day 10
Please write the calendar date that corresponds to each day of your trip. Day 1 is your first day of arrival in the country.					
Number of tablets taken in the morning (maximum 4)					
Number of tablets taken in the afternoon/evening (maximum 4)					
Symptoms in the prior 24 hours (check off all that apply)
Fever					
Nausea					
Vomiting					
Loose stools (less than three in a 24 hour period)					
Diarrhea (three or more loose stools in 24 hours)					
Bloody diarrhea					
Constipation					
Dark or black stool					
Dark or black tongue					
Abdominal pain					
Abdominal cramps					
Urgency to relieve oneself (in reference to stool)					
Bloating					
Flatulence/gas					
Congestion/runny nose					
Sore throat					
Cough					
Rash					
Headache					
Dizziness					
Ringing in your ears					
Muscle pain/soreness					
Joint pain/swelling/redness					
Drowsiness (severe)					
Confusion					
Depression					

Other (list/describe):					
Medical care
Did you seek medical care for one or more of these symptoms? (Yes/No/Don't Know)	Y N D	Y N D	Y N D	Y N D	Y N D
→ If yes, where? (check the corresponding box(es))
A doctor's office					
Urgent care clinic (outpatient)					
Emergency room					
Hospital outpatient clinic setting					
Hospital inpatient ward – hospitalized					
Other (specify)					
→ Was your diagnosis travelers' diarrhea? (Yes/No/Don't Know)	Y N D	Y N D	Y N D	Y N D	Y N D
Have you started any medications in the past 24 hours? (Yes/No/Don't Know)	Y N D	Y N D	Y N D	Y N D	Y N D
→ If yes, what medication(s)?					
→ Please circle those that were provided for you at your pre-travel consultation with the study clinic.
What city(ies) and country(ies) have you been in during the past 24 hours? Please write answers to all questions in the corresponding box.					
Have you eaten any of the following in the past 24 hours? (Yes/No/Don't Know)
→ Fermented or pickled foods (e.g., bean paste, fish kimchi, etc.)	Y N D	Y N D	Y N D	Y N D	Y N D
→ Yogurt	Y N D	Y N D	Y N D	Y N D	Y N D
Comments:					

PARTICIPANT UNIQUE ID: _____

GROUP ID: _____

	Day 11	Day 12	Day 13	Day 14	Day 15
Please write the calendar date that corresponds to each day of your trip. Day 1 is your first day of arrival in the country.					
Number of tablets taken in the morning (maximum 4)					
Number of tablets taken in the afternoon/evening (maximum 4)					
Symptoms in the prior 24 hours (check off all that apply)
Fever					
Nausea					
Vomiting					
Loose stools (less than three in a 24 hour period)					
Diarrhea (three or more loose stools in 24 hours)					
Bloody diarrhea					
Constipation					
Dark or black stool					
Dark or black tongue					
Abdominal pain					
Abdominal cramps					
Urgency to relieve oneself (in reference to stool)					
Bloating					
Flatulence/gas					
Congestion/runny nose					
Sore throat					
Cough					
Rash					
Headache					
Dizziness					
Ringing in your ears					
Muscle pain/soreness					
Joint pain/swelling/redness					
Drowsiness (severe)					
Confusion					
Depression					

Other (list/describe):					
Medical care
Did you seek medical care for one or more of these symptoms? (Yes/No/Don't Know)	Y N D	Y N D	Y N D	Y N D	Y N D
→ If yes, where? (check the corresponding box(es))
A doctor's office					
Urgent care clinic (outpatient)					
Emergency room					
Hospital outpatient clinic setting					
Hospital inpatient ward – hospitalized					
Other (specify)					
→ Was your diagnosis travelers' diarrhea? (Yes/No/Don't Know)	Y N D	Y N D	Y N D	Y N D	Y N D
Have you started any medications in the past 24 hours? (Yes/No/Don't Know)	Y N D	Y N D	Y N D	Y N D	Y N D
→ If yes, what medication(s)?					
→ Please circle those that were provided for you at your pre-travel consultation with the study clinic.
What city(ies) and country(ies) have you been in during the past 24 hours? Please write answers to all questions in the corresponding box.					
Have you eaten any of the following in the past 24 hours? (Yes/No/Don't Know)
→ Fermented or pickled foods (e.g., bean paste, fish kimchi, etc.)	Y N D	Y N D	Y N D	Y N D	Y N D
→ Yogurt	Y N D	Y N D	Y N D	Y N D	Y N D
Comments:					

PARTICIPANT UNIQUE ID: _____

GROUP ID: _____

	Day 16	Day 17	Day 18	Day 19	Day 20
Please write the calendar date that corresponds to each day of your trip. Day 1 is your first day of arrival in the country.					
Number of tablets taken in the morning (maximum 4)					
Number of tablets taken in the afternoon/evening (maximum 4)					
Symptoms in the prior 24 hours (check off all that apply)
Fever					
Nausea					
Vomiting					
Loose stools (less than three in a 24 hour period)					
Diarrhea (three or more loose stools in 24 hours)					
Bloody diarrhea					
Constipation					
Dark or black stool					
Dark or black tongue					
Abdominal pain					
Abdominal cramps					
Urgency to relieve oneself (in reference to stool)					
Bloating					
Flatulence/gas					
Congestion/runny nose					
Sore throat					
Cough					
Rash					
Headache					
Dizziness					
Ringing in your ears					
Muscle pain/soreness					
Joint pain/swelling/redness					
Drowsiness (severe)					
Confusion					
Depression					

Other (list/describe):					
Medical care
Did you seek medical care for one or more of these symptoms? (Yes/No/Don't Know)	Y N D	Y N D	Y N D	Y N D	Y N D
→ If yes, where? (check the corresponding box(es))
A doctor's office					
Urgent care clinic (outpatient)					
Emergency room					
Hospital outpatient clinic setting					
Hospital inpatient ward – hospitalized					
Other (specify)					
→ Was your diagnosis travelers' diarrhea? (Yes/No/Don't Know)	Y N D	Y N D	Y N D	Y N D	Y N D
Have you started any medications in the past 24 hours? (Yes/No/Don't Know)	Y N D	Y N D	Y N D	Y N D	Y N D
→ If yes, what medication(s)?					
→ Please circle those that were provided for you at your pre-travel consultation with the study clinic.
What city(ies) and country(ies) have you been in during the past 24 hours? Please write answers to all questions in the corresponding box.					
Have you eaten any of the following in the past 24 hours? (Yes/No/Don't Know)
→ Fermented or pickled foods (e.g., bean paste, fish kimchi, etc.)	Y N D	Y N D	Y N D	Y N D	Y N D
→ Yogurt	Y N D	Y N D	Y N D	Y N D	Y N D
Comments:					

PARTICIPANT UNIQUE ID: _____

GROUP ID: _____

	Day 21
Please write the calendar date that corresponds to each day of your trip. Day 1 is your first day of arrival in the country.	
Number of tablets taken in the morning (maximum 4)	
Number of tablets taken in the afternoon/evening (maximum 4)	
Symptoms in the prior 24 hours (check off all that apply)	...
Fever	
Nausea	
Vomiting	
Loose stools (less than three in a 24 hour period)	
Diarrhea (three or more loose stools in 24 hours)	
Bloody diarrhea	
Constipation	
Dark or black stool	
Dark or black tongue	
Abdominal pain	
Abdominal cramps	
Urgency to relieve oneself (in reference to stool)	
Bloating	
Flatulence/gas	
Congestion/runny nose	
Sore throat	
Cough	
Rash	
Headache	
Dizziness	
Ringing in your ears	
Muscle pain/soreness	
Joint pain/swelling/redness	

Drowsiness (severe)	
Confusion	
Depression	
Other (list/describe):	
Medical care	
Did you seek medical care for one or more of these symptoms? (Yes/No/Don't Know)	Y N D
→ If yes, where? (check the corresponding box(es))	...
A doctor's office	
Urgent care clinic (outpatient)	
Emergency room	
Hospital outpatient clinic setting	
Hospital inpatient ward – hospitalized	
Other (specify)	
→ Was your diagnosis travelers' diarrhea? (Yes/No/Don't Know)	Y N D
Have you started any medications in the past 24 hours? (Yes/No/Don't Know)	
→ If yes, what medication(s)?	
→ Please circle those that were provided for you at your pre-travel consultation with the study clinic.	...
What city(ies) and country(ies) have you been in during the past 24 hours? Please write answers to all questions in the corresponding box.	
Have you eaten any of the following in the past 24 hours? (Yes/No/Don't Know)	
→ Fermented or pickled foods (e.g., bean paste, fish kimchi, etc.)	Y N D
→ Yogurt	Y N D
Comments:	

Post-travel Questionnaire

PARTICIPANT UNIQUE ID: _____

GROUP ID: _____

1. Have you had any of the following symptoms since returning home from your trip (circle all that apply)?

Symptom	Duration (in days)
Fever	
Nausea	
Vomiting	
Loose stools (less than three in a 24 hour period)	
Diarrhea (three or more loose stools in 24 hours)	
Bloody diarrhea	
Constipation	
Dark or black stool	
Dark or black tongue	
Abdominal pain	
Abdominal cramps	
Fecal urgency	
Bloating	
Flatulence/gas	
Congestion/runny nose	
Sore throat	
Cough	
Rash	
Headache	
Dizziness	
Ringing in your ears	
Muscle pain/soreness	
Joint pain/swelling/redness	
Drowsiness (severe)	
Confusion	
Depression	
Other (list/describe):	
Don't know	...
I would rather not answer	...

2. Did you start taking any of the following medications since you arrived home (circle all that apply)?

- a. **Oral or intravenous (IV) antibiotics** (e.g., azithromycin [Zithromax], ciprofloxacin [Cipro], rifaximin [Xifaxan], doxycycline or minocycline, metronidazole [Flagyl], cotrimoxazole [Bactrim or Septra], penicillins [e.g., amoxicillin, Augmentin], or cephalosporins [e.g., Keflex])
- b. **Antidiarrheals** (e.g., bismuth subsalicylate [Pepto Bismol/Kaopectate])
- c. **Antimotility agents** (e.g., loperamide [Imodium])
- d. **H2 blocker** (e.g., ranitidine [Zantac], cimetidine [Tagamet], famotidine [Pepcid])
- e. **Proton pump inhibitor** (e.g., omeprazole [Prilosec], pantoprazole [Protonix], lansoprazole [Prevacid], esomeprazole [Nexium])
- f. **Other antacids** (e.g., calcium carbonate [Tums/Rolaids], Maalox/Mylanta)
- g. **Probiotics** (*Yogurts and other fermented dairy products are probiotics. Probiotics can also take the form of capsules, pills, or powders. Probiotics also include any foods or drinks labeled as containing "live and active cultures" or "probiotics"*)
- h. **Oral or intravenous steroids** (e.g., prednisone, hydrocortisone)
- i. **Local/natural or herbal remedies** (herbs, etc.)
- j. **Other:**

3. Did you experience any of the following at any point during your travels?

Symptom	(Yes/No/Don't Know)	If yes, what was the duration (in days)?
Ringing in your ears	Y N D	
Constipation	Y N D	
Dark or black stool	Y N D	
Dark or black tongue	Y N D	
Drowsiness	Y N D	
Nausea	Y N D	
Vomiting	Y N D	
Rash	Y N D	
Other (list/describe):		

4. Did you seek medical care for an illness since returning to the United States after your trip?

- a. Yes
- b. No
- c. Don't know
- d. I would rather not answer

If yes to question 4, where did you seek and receive care?

- a. A doctor's office
- b. Urgent care clinic (outpatient)
- c. Emergency room
- d. Hospital outpatient clinical setting
- e. Hospital inpatient ward – hospitalized
- f. Other (please specify)

If yes to question 4, what was/were your diagnosis/es?

If yes to question 4, were you told that your illness was related to travel?

- a. Yes
- b. No
- c. Don't know
- d. I would rather not answer

If yes to question 4, were you told that you had travelers' diarrhea?

- a. Yes
- b. No
- c. Don't know
- d. I would rather not answer

If yes to question 4, were you told that you had a bacteria that was resistant to antibiotics?

- a. Yes
- b. No
- c. Don't know
- d. I would rather not answer

5. Did you travel to any countries not discussed during your pre-travel visit?

- a. Yes
- b. No
- c. Don't know
- d. I would rather not answer

If yes to question 5, please list the new countries you visited, the location(s) visited, and the number of days in each country:

Country name	Specific location(s) to be visited (e.g., city/town, attraction)	Number of days in this country
1.		
2.		
3.		
4.		
5.		

6. Did you not travel to a country you discussed at your pre-travel visit?

- a. Yes

- b. No
- c. Don't know
- d. I would rather not answer

If yes to question 6, please list the countries you did not visit.

Country name
1.
2.
3.
4.
5.

7. Did the time you spent in each country change from what you reported at your pre-travel visit?

- a. Yes
- b. No
- c. Don't know
- d. I would rather not answer

If yes to question 7, please list the countries in which the amount of time spent changed, including the number of days actually spent in each country:

Country name	Number of days in this country
1.	
2.	
3.	
4.	
5.	

This survey is now completed.

Thank you very much for your time.

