Based upon published reports, we anticipate that participants in the intervention arm of the study will experience a health benefit; they will be less likely to acquire TD while abroad. They also may benefit, in the event that they do acquire TD, by having a shorter duration and lesser severity of TD symptoms in comparison to those in the placebo group.

Description of the Potential Risks to Anticipated Benefit Ratio

The potential benefits of participating in this study outweigh the minimal risks.

Emergency Care

We do not anticipate participants needing emergency care as a part of this study.

Participants will be provided phone and email contact information for study personnel in the event questions or concerns arise that may relate to their participation in the study.

Study Timeline

Table 1. Study Timeline, 2017–2020

Study Component	Date of Anticipated Start	Date of Anticipated End
Protocol Writing and Coordination	March 2017	October 2017
Submission of protocol/consent forms for IRB approval	November 2017	Late December 2017
Training of study personnel	January 2018	January 2018
Enrollment of participants	February 2018	July 2019
Laboratory analysis of stool specimens	February 2018	October 2019
Data entry	February 2018	October 2019
Data analysis (every 3 months)	April 2018	November 2019
Manuscript writing and clearance	November 2019	March 2020
Dissemination of findings	March 2020	

Study Population

Description and Source of the Study Population

Participants will be selected from persons seeking a pre-travel consultation at The New York Center for Travel and Tropical Medicine, New York, United States. This clinic serves travelers by providing pre-travel consultative services, in addition to post-travel screening, assessment, diagnostic, and treatment services. Centrally located in Manhattan, this clinic serves a large variety of international travelers, including tourists, immigrants or their relatives, and business travelers, among others. Travelers' destinations are equally varied, reflecting the ethnic and cultural diversity of New York City.

Definitions

Diarrhea:

≥ 3 unformed stools in 24 hours, with or without associated symptoms such as fever, cramping, or abdominal pain

Travelers' diarrhea:

Diarrhea that begins while traveling (after arrival in a country) or within 10 days after return

Study period:

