Once recruited and consented, eligible participants will be registered in the study at the clinic site and receive a one-page instructional handout regarding stool specimen collection and questionnaire completion [**APPENDIX K**]. All primary participant information will be kept at the clinic. Travelers will agree to inform the study personnel at their clinic site if they have a change in travel plans, begin a course of antibiotics, become pregnant before or during travel, or develop diarrhea before departure, to determine if they are still eligible to participate. In the event that a participant withdraws from the study at any time, the clinic must note this in the study database.

Description and Justification of Compensation

Gift card compensation will be provided to the participants for the time spent on this project.

The participant will receive \$100 for completion of the pre-travel questionnaire and the submission of a pre-travel biologic (stool) specimen. For each daily questionnaire that the participant completes while traveling, they will receive an additional \$5 (maximum additional \$100). The participant will receive an additional \$50 for completion of the web-based post-travel questionnaire and an additional \$50 for the submission of a biologic (stool) specimen post-travel. The maximum compensation will be \$300 total. The minimum participation to receive compensation is good medication compliance, good questionnaire compliance, and good biologic (stool) specimen compliance (see Definitions).

Compensation will be mailed to participants upon completion of their study period.

Statement of Extra Costs to Participants Due to their Involvement in the Study

We do not anticipate any extra costs to the participants due to their involvement.

Procedures for Implementing and Documenting Informed Consent

The New York Center for Travel and Tropical Medicine clinic must obtain and ensure scientific and ethical permission, in accordance with state and national regulations. All collaborators must adhere to strict guidelines to ensure participant confidentiality, following the Privacy Act. Biological specimens (stool) must be processed per established safety protocols.

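### Diarrhea during travel is recorded only as a tick with no negative answer, so a blank symptom block cannot be reliably told from a diarrhea-free day, and no rule says how to code it

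*Combined protocol and SAP*

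**What the plan says.** The Definitions section sets TD as "Diarrhea that begins while traveling (after arrival in a country) or within 10 days after return", where diarrhea means at least 3 unformed stools in 24 hours.

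In the during-travel questionnaire (Appendix D) the endpoint is one row, "Diarrhea (three or more loose stools in 24 hours", in a list introduced by "Symptoms in the prior 24 hours (check off all that apply". The layout repeats for Days 1 to 21. No row means none, and no symptom has a negative answer.

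Other items on the same form do have explicit Yes/No/Don't Know answers:
- care-seeking: "Did you seek medical care for one or more of these symptoms? (Yes/No/Don't Know"
- new medication in the past 24 hours
- foods: "Have you eaten any of the following in the past 24 hours"
- on Day 1 only, diarrhea before arrival: "Did you have any diarrhea between completing the pre-travel questionnaire and arriving in the country? (Yes/No/Don't Know"

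The post-travel questionnaire (Appendix E) opens with "Have you had any of the following symptoms since returning home from your trip (circle all that apply". It offers Don't know and a refusal option, but not None. Its item 3 asks Yes/No/Don't Know about eight named symptoms at any time during the trip, with a free-text row for others. Diarrhea is not among the eight.

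Questionnaire compliance (Definitions) is graded by the number of questionnaires completed. Payment is also per form: "For each daily questionnaire that the participant completes while traveling, they will receive an additional" amount of $5 (Description and Justification of Compensation). Neither place defines completion by item. Quality Control and Assurance has data entered as received and checked for completeness every 3 months, with no rule for a blank symptom block.

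**The concern.** A tick list records presence only. When the rest of the day is filled in and the symptom block is empty, the form does not show whether the participant had nothing to report or passed over the block. Both ways of coding the blank have a cost. If it counts as TD-free, any skipped diarrhea day becomes a favorable outcome. If it counts as missing, participants who were well and correctly ticked nothing lose those days. The sample size, stated for participants with full questionnaire compliance, then no longer refers to a group the form can identify.

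The same forms give foods, care-seeking and several trip side effects an explicit answer, but not the primary endpoint. What the form never asked cannot be fully recovered at analysis.

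**Working it through.** **1. Where could an unrecorded diarrhea day be recovered?**
- Other ticks that day: they show the block was opened, but help only if another symptom was present.
- TD diagnosis item (Appendix D): answered only if care was sought.
- New-medication item (Appendix D): helps only if a drug was started, and the drug must then be interpreted.
- Post-travel item 1: covers only the time since return.
- Post-travel item 3: covers the trip, but diarrhea could enter only as free text.

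The backstop is therefore partial.

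**2. Reproduce the planned sample size.** Inputs from Sample Size and Power Calculation: 40% on placebo, 30% protection, so 28% on BSS; alpha 0.05; power 80%. Sidedness is not stated; two-sided, pooled variance and no continuity correction reproduces the plan. With p̄ = 0.34:

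n per arm = [z₀.₉₇₅·√(2p̄(1−p̄)) + z₀.₈₀·√(p₁(1−p₁)+p₂(1−p₂))]² / (p₁−p₂)²

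= [1.960 × 0.6699 + 0.8416 × 0.6645]² / 0.12² = 243.4, rounded up to 244, or 488 in total. This matches the plan.

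Power at 244 = Φ{[0.12 × √244 − 1.960 × 0.6699] / 0.6645} = Φ(0.845) = 80.1%.

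**3. Equal loss in both arms (assumed).** Let m be the share of participants with TD who are recorded as TD-free. Both rates are multiplied by 1 − m.

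| m | Placebo | BSS | Relative risk | Power at 244 per arm | Total N for 80% |
|---|---|---|---|---|---|
| 0 | 40.0% | 28.0% | 0.70 | 80.1% | 488 |
| 5% | 38.0% | 26.6% | 0.70 | 77.0% | 526 |
| 10% | 36.0% | 25.2% | 0.70 | 73.7% | 570 |

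The odds ratio, which the table shells in Appendix I report, moves only from 0.583 to 0.599 at m = 10%.

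**4. From skipped days to lost cases.** TD is met by diarrhea on any day, so an episode is lost only if all of its days go unrecorded. With an independent daily skip rate s and an episode of D days, m = s^D. At an assumed s = 10%:
- D = 1: m = 10%, power 73.7%
- D = 2: m = 1%, power 79.5%
- D = 3: m = 0.1%, power 80.0%

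**5. Unequal loss (assumed).**
- 10% lost on placebo only: 36.0% vs 28.0%, apparent reduction 1 − 0.28/0.36 = 22%, power 47%.
- 10% lost on BSS only: 40.0% vs 25.2%, apparent reduction 1 − 0.252/0.40 = 37%, power 94%.
- No true effect, 40% in both arms, 10% lost in one arm: the two-sided rejection rate rises from 5% to about 15%.

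**The case against.** The strongest reply is that the plan never says a blank means no diarrhea. A reader might infer that skipped days are silently scored as successes and TD is therefore under-counted. The documents do not support that as a fact: they give no coding rule in either direction and no skip rate. That part of the reply stands.

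A reader might also infer that the problem is undetectable. It is not wholly so. Other ticks, the TD diagnosis item and the medication item help on some days, and all-blank days can be listed and varied in a sensitivity analysis. Nor do the compliance grades or the payment rule say that a day with a blank block counts as completed; they are silent.

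The participants whose skips would matter are those with something to tick, and longer episodes give them several chances. That also stands, and it limits the likely size.

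Finally, the REDCap build is not shown and the participant handout (Appendix K) is not in the text available, so required fields or instructions cannot be ruled in or out. This lowers confidence about the web version but does not settle the matter. Paper is an offered mode and cannot enforce a field, and a required tick list without a none option would leave a well participant with no valid answer.

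**Conclusion.** The concern holds as a gap in how the endpoint is captured and coded: a blank symptom block is ambiguous, no rule resolves it, and the post-travel form does not re-ask about diarrhea during the trip. A demonstrated under-count is not supported.

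All figures rest on assumed loss rates. Equal loss of 5% to 10% of TD cases would cost about 3 to 6 points of power and leave the relative risk unchanged. A larger fall, such as to 66.5%, needs 20% of all TD cases to go wholly unrecorded, which nothing in the documents suggests. For episodes of two days or more, a 10% independent daily skip rate costs less than one point.

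Unequal loss matters more, because it biases the estimate in either direction. Study Limitations accepts that dark stool or tongue may lead participants to guess their arm and that this could influence their answers. Whether it would change how often the symptom block is skipped is not documented.

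This should be fixed as a cheap improvement to the primary endpoint data. It does not show that the planned sample size is wrong.

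**What to change.** - **Appendix D, web and paper:** add an explicit daily Yes/No answer for diarrhea, keeping the present stool-count threshold and making it required in REDCap. Add a none-of-these box to the symptom list.
- **Appendix E:** in item 1, make diarrhea since return Yes/No/Don't Know and add a none-of-these option. Add diarrhea to item 3 as a look-back over the trip.
- **Coding rule:** state in Definitions or Data Handling and Analysis that a day without the diarrhea answer is missing, not TD-free, and is not a completed diary day. Paper forms depend on this rule because they cannot enforce a required field.

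Cost: a form revision, one IRB amendment, a few seconds per diary day, and slightly lower recorded completeness. The planned 488 does not change.

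### The 24-hour window in the diarrhea definition is unspecified and the diary stores no stool number or time, so 3- or 4-stool episodes spanning two entries may be scored as no TD

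*Combined protocol and SAP*

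**What the plan says.** The Definitions section gives diarrhea as "≥ 3 unformed stools in 24 hours, with or without associated symptoms such as fever, cramping, or abdominal pain", and TD as "Diarrhea that begins while traveling (after arrival in a country) or within 10 days after return". Neither says where the 24 hours start.

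During travel, the endpoint rests on the Appendix D diary. It has one column per dated trip day ("Please write the calendar date that corresponds to each day of your trip. Day 1 is your first day of arrival in the country"), headed "Symptoms in the prior 24 hours (check off all that apply". Two rows concern stool frequency: "Loose stools (less than three in a 24 hour period" and "Diarrhea (three or more loose stools in 24 hours". Both are tick boxes that the participant classifies alone. The form asks for no number of stools and no times, and sets no hour for completion.

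Little else would recover an in-travel episode. The item "Was your diagnosis travelers' diarrhea? (Yes/No/Don't Know" follows only from having sought care. In the post-travel questionnaire (Appendix E), item 1 covers symptoms since return. Item 3 looks back at the trip, but its printed list has no diarrhea row, only a free-text line for other symptoms. No section says how diary ticks become the TD endpoint or how adjacent days are combined; the Table 2 shell in Appendix I simply has a TD percentage column.

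**The concern.** A threshold on events within 24 hours can be applied to any rolling 24 hours or to each diary day separately. The two readings agree for heavy episodes and can disagree for light ones. Take a diary completed at 20:00 and loose stools at 18:00, 19:00, 22:00 and 02:00. On a rolling reading this is four stools in 8 hours and counts as TD. Counted entry by entry it is two and two, and both days may be ticked below three. With no counts or times stored, the analyst cannot tell this record from two days with one loose stool each.

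Any such loss falls on the primary endpoint. If it is equal in both arms, the event rates and the power fall. It need not be equal: the section on anticipated benefits expects BSS recipients who develop TD to gain "by having a shorter duration and lesser severity of TD symptoms in comparison to those in the placebo group", and light episodes are the ones at risk of being missed. The Hypotheses section asks separately whether BSS prevents TD (1a) and whether it reduces severity or frequency (1b), and the diary stores no stool count to help answer 1b.

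**Working it through.** **1. The plan's own figure.** Inputs from Sample Size and Power Calculation: p1 = 0.40, p2 = 0.40 × (1 − 0.30) = 0.28, alpha 0.05, power 80%. Sidedness is not stated; two-sided is assumed because it reproduces the figure. With p̄ = 0.34 and pooled variance under the null,

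n = [1.960 × √(2 × 0.34 × 0.66) + 0.842 × √(0.40 × 0.60 + 0.28 × 0.72)]² / 0.12² = 243.4, so 244 per arm and 488 in total, as stated. Power at 244 per arm is 80.1%.

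**2. Which episodes can be lost.** Assume that participants count strictly within each entry and that consecutive entries adjoin. A 24-hour cluster then touches at most two entries, and it is lost only if each holds at most two stools.
- 3 stools: lost when split 2+1 or 1+2.
- 4 stools: lost only when split 2+2.
- 5 or more: one entry must hold at least three, so none is lost.

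**3. Chance of a loss for one isolated cluster.** Let the first and last stools be L hours apart, the others uniform between them, and the diary time uniform over the day. With 3 stools, the diary time must fall anywhere between first and last: L/24. With 4, it must fall between the second and third, a mean gap of L/3: L/72.

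| Stools | L = 6 h | L = 12 h | L = 18 h |
|---|---|---|---|
| 3 | 25% | 50% | 75% |
| 4 | 8% | 17% | 25% |
| 5 or more | 0% | 0% | 0% |

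Simulation gave the same values.

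**4. Overall share lost.** This needs the distribution of stool counts and episode lengths, which the documents do not give. A simulation (a first stool, then Poisson further stools uniform over the episode, random diary time, strict counting per entry) shows how far the answer depends on the inputs chosen. Share of rolling-window TD missed:
- 1-day episodes: about 53%, 38%, 25%, 16% and 5% at 1, 2, 3, 4 and 6 further stools per day.
- 2-day episodes: about 11% and 4% at 3 and 4 per day.
- 3-day episodes: about 5% and 1% at 3 and 4 per day.

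These are assumed scenarios, so no single figure can be put forward as the loss or as its upper limit.

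**5. Illustrative effect on power.** Multiply both rates by (1 − m), with m an assumed loss equal in the two arms. The risk ratio stays at 0.70.

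| m | Rates | Power at 244 per arm | Total N for 80% |
|---|---|---|---|
| 0 | 0.400 vs 0.280 | 80.1% | 488 |
| 5% | 0.380 vs 0.266 | 77.0% | 526 |
| 10% | 0.360 vs 0.252 | 73.7% | 570 |

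The plan expects to enroll about 500 against 488 needed with full compliance, a margin of 12.

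**The case against.** The strongest reply is that no contradiction has been shown. The definition says in 24 hours, not in any 24 hours, and the diarrhea row of the diary repeats that threshold almost word for word. A participant with four loose stools overnight could properly tick it. The diary does not impose fixed blocks either: the look-back moves with the time of completion, so entries may overlap, which would rescue some clusters, or leave gaps, which would lose others. All of this stands. It is why the claim is that episodes may be missed, not that they are.

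The 40% planning rate may itself come from studies with similar daily diaries. In that case deducting a further loss counts it twice. The documents do not say how the rate was obtained, so the power figures hold only on the opposite assumption.

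A reader might also infer that the form makes BSS look better than it is. For instance, an assumed 10% loss on placebo and 20% on BSS gives 0.36 vs 0.28 × 0.80 = 0.224, a risk ratio of 0.622, and so 38% apparent protection instead of 30%. The direction is plausible given the expected milder TD. But nothing in the documents supports that split, and part of the effect, milder disease falling below a cut-off, belongs to any threshold endpoint. The 38% is pure illustration and should carry no weight.

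A lone tick for bloody diarrhea carries no count. Since participants may tick every row that applies, this is a possibility rather than a demonstrated failure.

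**Conclusion.** The point holds as a gap in specification and measurement of the primary endpoint. The window is undefined, stool number and time are not stored, no derivation rule is given, and no later questionnaire item asks directly about in-travel diarrhea. Where participants answer within each entry, 3- or 4-stool episodes spanning two entries may be scored as no TD, and the analyst cannot reconstruct them. With adjoining entries, episodes with 5 or more stools in the straddling 24 hours are safe.

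The size cannot be derived from the documents. The fall in power to between 77.0% and 73.7% rests on three assumptions: a loss of 5% to 10%, equality between arms, and a 40% rate free of similar loss. The documents do not support the stronger readings that the diary contradicts the definition, that such episodes are necessarily missed, or that efficacy will be overstated by a known amount. The correction is worth making because it is cheap and counts not taken during travel cannot be recovered later.

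**What to change.** - **Definitions:** state that the window is any 24 hours.
- **Appendix D, paper and REDCap:** record the number of loose stools per entry. Ask also whether three or more occurred within any 24-hour period, counting stools reported on the previous entry. Making blood a sub-item of this question is optional.
- **Analysis:** specify that during-travel TD is derived from the cross-entry question. The count supports question 1b. It is only a rough check on the cross-entry answer, because it carries no times.
- **Forms already collected:** an analysis that also counts consecutive days ticked for fewer than three loose stools may be reported, but only as an exploratory upper bound, with a statement that it will include many non-cases. In the model above, with 2-day episodes and 1 further stool per day, it flags about half of the non-cases, a little over two for each missed case recovered. At 3 per day the ratio is about 0.5.

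The cost is one extra number and one reworded question per day, the matching REDCap fields, and an IRB amendment, a route the plan already provides under Study Instruments.
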